## 2.3 Patient disposition, demographics, and other baseline characteristics

### 2.3.1 Demographics and baseline characteristics

FAS will be used for all baseline and demographic summaries and listings unless otherwise specified. Patient demographics and baseline characteristics collected will include the following: date of birth, gender (and childbearing potential for female), race and ethnicity, height, weight, all relevant medical history including cardiovascular disease history, CML disease history, including mutation status, and prior and concomitant medication including prior TKI therapy and antineoplastic medication.

Physical examination including, extramedullary involvement, performance status, vital signs, ECGs, and laboratory assessments performed at screening will be summarized by Cohort.

Summaries will be reported for all patients. No inferential statistics will be provided.

All demographic and baseline disease characteristics data will be summarized by Cohort. Categorical data (e.g., age groups: < 65, and  $\geq$  65 years, sex, race, ethnicity, ECOG performance status) will be summarized by frequency counts and percentages; the number and percentage of patients with missing data will be provided. Continuous data (e.g., age, weight, height, body mass index) will be summarized by descriptive statistics (N, mean, median, standard deviation, minimum and maximum), where BMI ( $\text{kg}/\text{m}^2$ ) will be calculated as  $\text{weight}[\text{kg}] / (\text{height}[\text{m}]^2)$  using weight at screening.

The number (%) of patients in each Cohort A, B & C (“With T315I Mutation” or “Without T315I Mutation”) based on data obtained from the IRT system will be summarized based on their respective assigned cohort for all the patients in their respective analysis sets.

### 2.3.2 Diagnosis and extent of cancer - CML

All diagnosis and extent of CML data will be summarized by Cohort. One summary table will include time (years) since initial diagnosis (descriptive statistics with N, mean, median, standard deviation, minimum and maximum) and historical mutation (frequency counts and percentages). Another table will include extramedullary involvement (frequency counts and percentages).

### 2.3.3 Medical history

Significant findings that were present prior to the signing of informed consent will be included in the Relevant Medical History/Current Medical Conditions page on the patient's eCRF. Significant new findings that begin or worsen after informed consent will be recorded on the AE page of the patient's eCRF and will be summarized & listed overall and by Cohort.

Medical history and ongoing conditions, including toxicity grade entered on eCRF will be summarized and listed by Cohort. The summary will be presented by primary system organ class (SOC), preferred term (PT) and Cohort. Medical history and current medical conditions will be coded using the Medical Dictionary for Regulatory Activities (MedDRA) terminology. The MedDRA version used for reporting will be specified in the CSR and as a footnote in the applicable tables/listings.

In addition, separate summary tables & listings will be produced for medical history possibly contributing to pulmonary diseases, and cardiovascular events.

### 2.3.4 Patient disposition

All randomly allocated patients by center will be summarized for all enrolled patients by Cohort using the FAS. The number (%) of enrolled patients included in the FAS will be presented overall and by Cohort. The number (%) of screened, enrolled and not - enrolled patients and the reasons for screening failure will also be displayed. The number (%) of patients in the FAS who are still on treatment, who discontinued the study phases and the reason for discontinuation will be presented overall and by Cohort.

The following summaries will be provided (with % based on the total number of FAS patients):

- Number (%) of patients who were enrolled (based on data from IRT system)
- Number (%) of patients who were enrolled but not treated (based on DAR eCRF page not completed for any study medication component)
- Primary reason for not being treated (based on “End of Screening Phase” and “Withdrawal of Informed Consent(s)” eCRF pages)
- Number (%) of patients who were treated (based on DAR eCRF pages of each study medication completed with non-zero dose administered)
- Number (%) of patients who completed the study medication (based on the “Completion of Treatment disposition phase” Disposition eCRF page)
- Number (%) of patients who discontinued the study medication (based on the “End of Treatment Disposition” page)
- Primary reason for study medication phase discontinuation (based on the “End of Treatment Disposition” page)
- Number (%) of patients who have entered the safety follow-up (based on the “Completed/Discontinuation of Post-Treatment follow-up” Disposition eCRF page)
- Number (%) of patients who completed the safety follow-up (based on the “Completion of Post-Treatment follow-up” Disposition eCRF page)
- Number (%) of patients who discontinued the safety follow-up (based on the “Discontinuation of post-Treatment follow-up” Disposition eCRF page)
- Primary reason for safety follow-up discontinuation (based on the “Discontinuation of post-Treatment follow-up” Disposition eCRF page)

Safety follow-up will not be reported in the disposition summary for primary analyses timepoint (24 weeks).

### 2.3.5 Protocol deviations

The number (%) of patients in all the analysis sets with CSR reportable protocol deviations will be tabulated by deviation category (as specified in the Study Specification Document) overall and by Cohort. All CSR reportable protocol deviations will be listed.

## 2.4 Treatments (study medication, rescue medication, concomitant therapies, compliance)

### 2.4.1 Duration of exposure to study medication

The safety set (SS) will be used for all summaries of study medication.

The duration of exposure will be summarized for each study cohort A, B and C. The dose intensity (computed as the ratio of actual cumulative dose received and actual duration of exposure) and the relative dose intensity (computed as the ratio of dose intensity and planned dose intensity) will be summarized for each study cohort by descriptive statistics.

- The number of participants will be summarized for SS by study cohort.
- The number (%) of patients who have dose reductions or interruptions, and the reasons, will be summarized by cohort.
- Patient level listings of all doses administered on medication along with dose change reasons will be produced.
- Duration of exposure to study medication is considered by taking into account the duration of exposure of non-zero doses to the investigational drug or control.
- Time on treatment(weeks) = [(date of last administration of study medication) – (date of first administration of study medication) – (days with zero dose) + 1] / 7.
- Duration of exposure to study treatment (weeks) = [(date of last administration of study medication) – (date of first administration of study medication) + 1] / 7.
- The date of last administration of study medication is defined in [Section 2.1.1](#).
- Summary of duration of exposure of study medication will include categorical summaries based on intervals (<24 weeks, ≥24 weeks and < 48 weeks, ≥48 weeks and < 72 weeks, ≥72 weeks) and continuous summaries (i.e., mean, standard deviation etc.).

### Cumulative dose

Cumulative dose of a study medication is defined as the total dose given during the study medication exposure.

The **planned cumulative dose** for a study medication refers to the total planned dose as per the protocol up to the last date of study medication administration. The calculations for the three separate doses of study medication are:

- Cohort A (ABL001): 40 mg/administration × 2 (administration/day) × duration of exposure (days)
- Cohort B (ABL001): 80 mg/administration × 1 (administration/day) × duration of exposure (days)
- Cohort C (ABL001): 200 mg/administration × 2 (administration/day) × duration of exposure (days)

The **actual cumulative dose** refers to the total actual dose administered, over the duration for which the patient is on the study medication as documented in the DAR eCRF. It is the sum of the non-zero total daily doses recorded over the dosing period. For patients who did not take any drug the actual cumulative dose is by definition equal to zero. The actual cumulative dose will be summarized for each of the Cohort.

## **Dose intensity and relative dose intensity**

**Dose intensity (DI)** for patients with non-zero duration of exposure is defined as follows: DI (mg/day) = Actual cumulative dose (mg) / Duration of exposure to study treatment(days).

For patients who did not take any drug the DI is by definition equal to zero.

**Planned dose intensity (PDI)** is defined as:

PDI (mg/day) = Planned cumulative dose (mg) / Duration of exposure to study treatment(days).

**Relative dose intensity (RDI (%))** is defined as follows:

RDI (%) = [DI (mg/day) / PDI (mg/day)]\*100.

DI and RDI (%) will be summarized separately for all the three study Cohorts.

## **Dose changes, interruptions or permanent discontinuations**

The number of patients, who have dose reductions, dose interruptions or permanent discontinuations, and the reasons, will be summarized separately for all the three study cohorts.

‘Dose Reduced’, ‘Dose Interrupted’ and ‘Dose Permanently Discontinued’ fields from the DAR eCRF pages will be used to determine the dose reductions, dose interruptions, and permanent discontinuations, respectively.

The corresponding fields, ‘Reason for Dose Reduction’, ‘Reason for Dose Interruption and ‘Reason for Permanent Discontinuation’ will be used to summarize the reasons.

A dose change occurs when total daily dose is different from the most recently planned dose. For patients in Cohort A, there is only one planned dose, i.e., 40 mg b.i.d. For patients in Cohort B, there is only one planned dose, i.e., 80 mg/day QD. For patients in Cohort C, the initial planned dose is 200 mg b.i.d i.e., 400 mg/day.

For summarizing interruptions and reasons, multiple entries for interruption that are entered on consecutive days with different reasons will be counted as separate interruptions. However, if the reason is the same in the mentioned multiple entries on consecutive days, then it will be counted as one interruption.

**Reduction:** A dose reduction is where the actual total daily dose is lower than the most recently planned dose. Therefore, any dose reduction to correct a dosing error will not be considered a dose reduction. Only dose reduction is collected in the eCRF and will be summarized for the patient’s data available.

### **2.4.2 Prior, concomitant and post therapies/medication**

#### **Prior antineoplastic therapy/medications**

The number and percentage of patients who received any prior anti-neoplastic therapy /medications will be summarized by cohort and also for the lowest anatomical therapeutic classification (ATC) class and preferred term. Summaries will include total number of regimens.

Anti-neoplastic medications will be coded using the WHO Drug Dictionary (WHO-DD). Details regarding WHO-DD version will be included in the footnote in the tables/listings.

The above analyses will be performed using the SS.

### **Post treatment anti-neoplastic therapy/medication**

The number and percentage of patients who received any anti-neoplastic medication and/or therapy since discontinuation of study medication will be summarized by cohort for setting (e.g., adjuvant, metastatic, etc.) and for the lowest anatomical therapeutic classification (ATC) class and preferred term. Summaries will include total number of regimens, reason for initiation of new therapy, indication, route of administration and reason for discontinuation of therapy.

Anti-neoplastic medications will be coded using the WHO-DD. Details regarding WHO-DD version will be included in the footnote in the tables/listings.

The above analyses will be performed using the SS.

### **Prior and Concomitant therapies/Medications**

Prior and Concomitant therapies/medications are defined as all interventions (therapeutic treatments and procedures) other than the study medication administered to a patient coinciding with the study medication period. Prior therapies include medications (other than study drugs) and medical procedures started and ended prior to the start date of study medication. Concomitant therapies include medications (other than study drugs) and medical procedures starting on or after the start date of study medication but no later than 30 days after last dose of study medication or starting prior to the start date of study medication and continuing after the start date of study medication.

Prior and Concomitant therapies/medications will be coded using the World Health Organization (WHO) Drug Reference Listing (DRL) dictionary that employs the WHO ATC classification system and summarized by the lowest ATC class and PT using frequency counts and percentages. Surgical and medical procedures will be coded using MedDRA and summarized by SOC and PT. These summaries will include:

- Prior therapies/medications started and ended prior to the start date of study medication.
- Concomitant therapies/medications:
  1. Therapies/medications starting on or after the start of study medication but no later than 30 days after last dose of study medication and
  2. Therapies/medications starting prior to start of study medication and continuing after the start of study medication.

All prior & concomitant therapies/medications will be listed. Any concomitant therapies/medications starting and ending prior to the start of study medication or starting more than 30 days after the last date of study medication will be flagged in the listing. The safety set will be used for all concomitant therapies/medications' tables and listings.

### **2.5 Analysis of the primary objective**

The primary objective is to evaluate safety profile of monotherapy asciminib in CML-CP in 3L and beyond for Cohorts A, and B. For all primary safety analyses, the Safety Set (SS) will be used, unless stated otherwise.

The variables for the primary analysis are incidence and severity of AEs and SAEs, changes in laboratory values and vital signs, incidence of notable ECG abnormalities.

### **2.5.1 Primary endpoint**

The primary endpoint is to evaluate the safety profile of monotherapy asciminib (ABL001) with AEs, SAEs and laboratory studies' assessment during 24 weeks of therapy in CML-CP patients, for Cohorts A and B i.e., without T315I mutation status. All safety analyses will be based on the safety set (SS).

AE summaries will include all AEs occurring during on-treatment period. All AEs collected in the AE eCRF page will be listed along with the information collected on those AEs e.g., AE relationship to study drug, AE outcome, etc. AEs with start date outside of on-treatment period will be flagged in the listings.

AEs will be summarized by number and percentage of patients having at least one AE, having at least one AE in each primary system organ class (SOC) and for each preferred term (PT) using MedDRA coding. A patient with multiple occurrences of an AE will be counted only once in the respective AE category. A patient with multiple CTCAE grades for the same preferred term will be summarized under the maximum CTCAE grade recorded for the event. AE with missing CTCAE grade will be included in the 'All grades' column of the summary tables. Abnormal lab findings, vital signs and notable ECG abnormalities will also be summarized by cohort as explained in Safety analysis section 2.6.

### **2.5.2 Statistical hypothesis, model, and method of analysis**

No formal hypothesis testing is planned for this study.

For all safety analyses, the safety set will be used.

### **2.5.3 Handling of missing values**

Missing data for measures of safety will not be imputed.

## **2.6 Safety analyses**

All safety analyses will be based on the safety set (SS). All listings and tables will be presented by Cohort.

### **2.6.1 Adverse events (AEs)**

All the adverse events reported after administration of study drug to 30 days after the last date of drug to the patient are known as treatment emergent adverse events (TEAEs).

The summary tables for adverse events (AEs) will summarize only on-treatment events, with a start date during the on-treatment period (*treatment-emergent* AEs). In addition, a separate summary for death including on-treatment deaths will be provided. All AE will be listed and those collected during the on-treatment period (TEAE) will be flagged.

TEAEs will be summarized by number and percentage of patients having at least one AE in each primary system organ class (SOC) and for each preferred term (PT) using MedDRA coding. A patient with multiple occurrences of an AE will be counted only once in the respective AE category. A patient with multiple CTCAE grades for the same preferred term will be summarized under the maximum CTCAE grade recorded for the event. TEAE with missing CTCAE grade will be included in the 'All grades' column of the summary tables.

In TEAE summaries, the primary system organ class will be presented alphabetically, and the preferred terms will be sorted within primary SOC in descending frequency. The sorting order for the preferred term will be based on their frequency in the ABL001 arm Cohort A.

The following treatment emergent adverse event summaries will be produced by Cohort:

- Overview of TEAEs and deaths

- TEAEs by SOC and PT
- Summary by relationship
- Seriousness
- Leading to treatment discontinuation
- Leading to dose interruption/adjustment
- Requiring additional therapy and leading to fatal outcome

For posting to ClinTrial.gov and EudraCT, a summary table of on-treatment deaths and serious AEs and another summary table of non-serious AEs by treatment, both including occurrences (an occurrence is defined as >1 day between start and prior end date of record of same preferred term) and sorted by SOC and PT, will be presented as well.

All the adverse events will be graphically displayed by Cohorts using bar chart.

## **2.6.2 Adverse events of special interest / grouping of AEs**

### **Data analysis of AESIs**

An adverse event of special interest (AESI) are defined as adverse events (serious or non-serious) which are of scientific and medical concern specific to compound ABL001 as mentioned in Table 5-5. For which ongoing monitoring and rapid communication by the investigator to the sponsor may be appropriate. Such events may require further investigation in order to characterize and understand them.

Adverse events of special interest are defined on the basis of an ongoing review of the safety data. The latest approved version of CRS prior to the respective database lock will be used.

For each specified AESI, number and percentage of patients with at least one event of the AESI occurring during the on-treatment period will be summarized.

Summaries of these AESIs will be provided by cohort. If sufficient number of events occurred, analysis of time to first occurrence will be applied.

A listing of all grouping levels down to the MedDRA PTs used to define each AESI will be generated.

### **2.6.3 Deaths**

Separate summaries for on-treatment / TEAE and all deaths will be produced by system organ class and preferred term, by cohort.

All deaths will be listed, where on treatment deaths will be flagged. A separate listing of deaths prior to starting treatment will be provided for all screened patients.

## 2.6.5 Other safety data

### 2.6.5.1 ECG and cardiac imaging data

12-lead ECGs including PR, QRS, QT, QTcF and RR intervals will be obtained centrally for each patient during the study. ECG data will be read and interpreted centrally.

Absolute values/change from baseline will be summarized over time. As appropriate, the number and percent of patients will be tabulated by category. In addition, a listing of patients with at least one notable ECG value will be produced.

#### Data handling

The average of the triplicate ECG parameters at each time point will be used in the analyses.

#### Data analysis

The number and percentage of patients with notable ECG values will be presented by Cohort. Notable values are defined below:

- QT, QTcF
  - New value of  $> 480$  and  $\leq 500$  ms
  - New value of  $> 500$  ms
- HR
  - Increase from baseline  $> 25\%$  and to a value  $> 100$  bpm
  - Decrease from baseline  $> 25\%$  and to a value  $< 50$  bpm

- PR
  - Increase from baseline >25% and to a value > 200 ms
  - New value of > 200 ms
- QRS
  - Increase from baseline >25% and to a value > 120 ms
  - New values of QRS > 120 ms

A listing of only the patients with notable ECG values will be produced. In the listing the assessments collected during the on-treatment period will be flagged.

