Please refer to (Hughes, 2019) and the latest [Asciminib Investigator's Brochure] for more details.

Safety:

Asciminib was generally well tolerated in heavily pre-treated CML patients resistant to or intolerant of prior TKIs. As of March 2020, 239 patients were evaluable for safety. Seventy six study discontinuations have been reported; the most frequent reason for discontinuation was progressive disease, reported in 38 patients (15.9%). Adverse events leading to treatment discontinuation were reported in 15 patients (6.3%). Death leading to treatment discontinuation was reported in 3 patients (1.3%) (one patient in asciminib 20 mg BID due to aspiration pneumonia after bypass procedure and two patients with ALL with 80 mg and 160 mg BID due to progressive disease).

Among the 150 patients treated with asciminib monotherapy, almost all (94.7%) patients reported at least one AE, including 49.3% reported grade 3/4 AEs. The most common AEs (> 10%) among patients treated with 40 mg BID (n=35), regardless of study drug-relationship, were increased lipase, fatigue, diarrhea, thrombocytopenia, neutropenia, arthralgia, rash, headache, increased amylase, nausea, vomiting, abdominal pain, pyrexia, upper respiratory tract infection, back pain, hypertension, cough, pruritus, pain in extremity, dyspnea, bone pain, peripheral oedema, non-cardiac chest pain and insomnia. The most common reported grade 3/4 event was increased lipase (17.1%).

Forty-seven of 150 patients with CML-CP or CML-AP treated with asciminib single agent (31.3%) were reported with serious adverse events (SAE).

Electrocardiogram (ECG) data shows no reported QT prolongation (increase > 60 msec or new > 500 msec) in 40 mg BID asciminib monotherapy group. There were no reports of QT prolongation (increase > 60 msec) and two reports of new >500 msec (one each in 80 mg QD and 120 mg QD) among all asciminib monotherapy group.

Please refer to the latest [Asciminib Investigator's Brochure] for more details.

Pharmacokinetics:

PK data from 190 patients were available from the [CABL001X2101] study, as of 01-Sep-2017. When given as a single agent on a twice daily schedule, patients received escalating doses of asciminib ranging from 10 to 200 mg.

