6.5.2.1 Dose adjustments for QTcF prolongation

If QTcF >500 msec or QTcF prolongation >60 msec from baseline is observed at any point during study treatment, and confirmed, the below guidance must be followed:

1. Assess the quality of the ECG recording and the QT value and repeat if needed
2. Interrupt study treatment until confirmed resolution of QTcF and as per dose reduction guidelines for non-hematological AEs.
3. Determine the serum electrolyte levels (in particular hypokalemia and hypomagnesemia). If abnormal, correct abnormalities before resuming study treatment.
4. Review concomitant medication associated with QT prolongation, including drugs with a “Known”, “Possible”, or “Conditional risk of Torsades de Pointes” (refer to www.crediblemeds.org/), and drugs with the potential to increase the risk of study drug exposure related QT prolongation.
5. Check the dosing schedule and treatment compliance

After confirming ECG reading at site, if QTcF > 500 msec

- Interrupt study treatment
- Repeat ECG and confirm ECG diagnosis by a cardiologist or central ECG lab
- If QTcF confirmed > 500 msec:
 - Correct electrolytes, eliminate culprit concomitant treatments, and identify clinical conditions that could potentially prolong the QT as per the ECG and QTc Clinical Safety Standards Guidelines
 - Consult with a cardiologist (or qualified specialist)
 - Increase cardiac monitoring as indicated, until the QTcF returns to ≤ 480 msec
- After resolution to ≤ 480 msec, consider re-introducing treatment at reduced dose, and increase ECG monitoring (e.g., pre dose and 2 hours post dose after one week and two weeks of treatment re-introduction)
- If QTcF remains ≤ 500 msec after dose reduction, continue planned ECG monitoring during subsequent treatment
- If QTcF recurs > 500 msec after dose reduction, discontinue subject from trial

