### Baseline

For safety & efficacy evaluations, the last available assessment on or before the date of start of study medication of asciminib (40 mg BID, 80 mg QD & 200 mg BID) is taken as “baseline” assessment. For pre-dose electrocardiogram (ECG), the last available assessment before the treatment start date/time is used for baseline.

For ECGs, where study requires multiple replicates per time point, the average of these measurements would be calculated for baseline (if not already available in the database).

In rare cases where multiple laboratory measurements meet the baseline definition, with no further flag or label that can identify the chronological order, then the following rule should be applied: If values are from central and local laboratories, the value from central assessment should be considered as baseline.

If patients have no value as defined above, the baseline result will be missing.

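### The SAP's notable-ECG list has no QTcF change-from-baseline category, so a rise above 60 ms that ends at or below 480 ms meets no QTcF criterion in the count or the listing

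*SAP*

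**What the plan says.** SAP 2.6.5.1 sets the patient-level ECG output: "The number and percentage of patients with notable ECG values will be presented by Cohort. Notable values are defined below". The QT/QTcF entry has two categories, a new value above 480 and up to 500 ms and a new value above 500 ms. In the same list HR, PR and QRS each have a criterion relative to baseline; QT/QTcF does not. The accompanying listing is limited to patients with a notable value.

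The section also plans by-visit summaries ("Absolute values/change from baseline will be summarized over time") and leaves room for more: "As appropriate, the number and percent of patients will be tabulated by category". Neither it nor Protocol 12.7.4, which has the same general provision, names a QTcF change category or cut-off. The analysis values are means: "The average of the triplicate ECG parameters at each time point will be used in the analyses". For baseline replicates, SAP 2.1.1 says "the average of these measurements would be calculated for baseline".

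Elsewhere the protocol uses a change criterion. Section 6.5.2.1 opens its guidance with "If QTcF >500 msec or QTcF prolongation >60 msec from baseline is observed at any point during study treatment", subject to confirmation. Section 1.1.2.2 describes the earlier study in the same two-part form: "no reported QT prolongation (increase > 60 msec or new > 500 msec) in 40 mg BID asciminib monotherapy group". Protocol 12.4 and SAP 2.5 both name the incidence of notable ECG findings among the primary-analysis variables.

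**The concern.** The notable-ECG list decides who is counted in a primary-analysis variable for Cohorts A and B. The protocol uses two QTcF criteria, one for level and one for change, both as triggers for action and in describing earlier data. The SAP keeps the level criterion, adds a band below it, and has no counterpart to the change criterion. A patient who crosses the 60 ms threshold from a low baseline can therefore be missing from both the count and the listing.

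Two things are at stake. The reported incidence may omit patients with a QTcF change that the protocol itself regards as needing action. In addition, this study's results could be set beside the earlier report only on the half concerning new values above 500 ms, since the half concerning increases above 60 ms has no pre-specified patient count.

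Neither protocol section binds the SAP's analysis categories, so this is an analysis choice and not an inconsistency between the documents.

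**Working it through.** The plan states no figure on this point, so there is nothing to reproduce first. The check applies the SAP's two QTcF categories to the eligible baseline range and asks which rises above 60 ms fall outside both.

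**Inputs**
- Notable QTcF: above 480 and up to 500 ms, or above 500 ms (SAP 2.6.5.1).
- Change criterion: above 60 ms from baseline (Protocol 6.5.2.1 and 1.1.2.2).
- Eligible screening QTcF: below 450 ms for men and below 460 ms for women (Protocol 5.2, exclusion 3).

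**Where the gap lies.** A value meets neither QTcF category if it is at or below 480 ms. A rise above 60 ms can end there only if baseline + 60 < 480, so baseline < 480 − 60 = 420 ms. That is well inside the eligible range. The uncounted band runs from above 60 ms up to (480 − baseline) ms. In whole milliseconds:

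| Baseline (ms) | Rises above 60 ms meeting no QTcF category | On-treatment values |
|---|---|---|
| 380 | 61 to 100 ms | 441 to 480 |
| 400 | 61 to 80 ms | 461 to 480 |
| 410 | 61 to 70 ms | 471 to 480 |
| 419 | 61 ms only | 480 |
| 420 and above | none | – |

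Example: 400 to 465 ms is a rise of 465 − 400 = 65 ms and ends below 480 ms, so it meets no QTcF category. From a baseline of 420 ms upward, any rise above 60 ms ends above 480 ms and is counted as a level, though not identified as a change.

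**How common such rises might be.** The documents give no QTcF distribution, so the number of affected patients cannot be computed. Protocol 1.1.2.2 reports no increases above 60 ms in any monotherapy group but states no ECG denominator. With zero events in n patients, the one-sided 95% upper bound is 1 − 0.05^(1/n). The denominators below are assumptions:

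- n = 35, the number at 40 mg BID in the adverse-event summary, if all had evaluable ECGs: 1 − 0.05^(1/35) = 8.2%.
- n = 100, pooled doses: 1 − 0.05^(1/100) = 2.95%.
- n = 150, pooled doses, all monotherapy patients: 1 − 0.05^(1/150) = 1.98%.

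These bound all rises above 60 ms. The uncounted group is a subset, so the bounds cover it but do not measure it. They are not predictions, and none is offered for Cohort B or Cohort C.

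**The case against.** The strongest reply is that such patients would surface elsewhere. Under Protocol 6.5.2.1 a confirmed rise above 60 ms leads to treatment interruption. Under Protocol 10.1.1 a test result that forces a change in study medication is an adverse event. Handled as written, the case should reach the QTc-prolongation count among the events of special interest (SAP 2.6.2 and 5.4) and the interruption summary with reasons (SAP 2.4.1). This largely stands as a description of what ought to happen. It depends, however, on confirmation, action and reporting at the site; Protocol 8.3.2.1 requires adverse-event recording only for ECG findings judged clinically significant; and the result would not separate rises above 60 ms from other QTc events. It is not a count from central readings.

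Other points have partial force:

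- **By-visit summaries.** SAP 2.1 includes the maximum among its descriptive statistics. A maximum change at or below 60 ms at every visit would show that the summarised visits contain no such rise. A maximum above 60 ms would not say how many patients had one.
- **Discretionary tabulation.** A change table is permitted, but no cut-off is defined, so it could be chosen after the data are seen.
- **Other ECG criteria.** An uncorrected QT above 480 ms, or an HR, PR or QRS criterion, could flag some of these patients, but not as a QTcF rise.
- **Confirmation.** The protocol trigger requires it and the proposed row does not, so the two would not count exactly the same patients. The existing notable categories also use triplicate means without a confirmation step, so the row would be consistent with its own table.
- **Earlier data.** They show no rises above 60 ms but two new values above 500 ms, one of them at 80 mg QD. The SAP also adds the band from 480 to 500 ms, and its two levels together capture every rise above 60 ms from a baseline of 420 ms or more. This supports a low rating. It does not close the gap below 420 ms.

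**Conclusion.** The concern holds and is minor. Followed exactly, the SAP leaves out of its QTcF categories any patient with a baseline below 420 ms who rises by more than 60 ms and stays at or below 480 ms. No pre-specified output counts rises above 60 ms from the central readings.

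The likely size is zero to a few patients, an expectation that rests on the absence of such rises in the earlier data. That absence is limited reassurance: at 40 mg BID it is compatible with a rate of up to 8.2% if all 35 patients had evaluable ECGs. The stated primary endpoint is adverse events, serious adverse events and laboratory evaluation. The ECG count is a descriptive variable within the primary analysis, and no hypothesis test depends on it.

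**What to change.** In SAP 2.6.5.1, add a category for QTcF increase from baseline above 60 ms, based on triplicate means, to the notable-ECG table and listing for all three cohorts. State that scheduled and unscheduled on-treatment ECGs both count; SAP 2.1 already includes all data collected up to the cut-off, so this only makes the rule explicit.

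Label the row post hoc in any output already locked, such as the 24-week output if its lock has passed. Pre-specify it for outputs not yet locked, such as the 72-week safety summary under SAP 2.8.1.

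The cost is one row and one listing criterion. Triplicate means, a mean baseline and change from baseline are already planned, so no new data collection or hypothesis test is needed. The change concerns reporting only and leaves Protocol 6.5.2.1 as it is.
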